### **Ascertainment of study outcomes - at all sites:**

Ultimately, in the intervention sites we will be able to use the newly developed and introduced Contact Management Registries (see below) to extract all necessary information and outcomes – including number of pulmonary TB cases (Index cases), number of contacts identified, and number who initiate LTBI therapy. However, these detailed contact registries are considered an integral part of the public health intervention, since considerable training in recording and reporting as well as the procedures of contact management will be needed for these to be completed accurately and completely. Introduction of these registries at control sites would be difficult without extensive training; if such training was given at the control sites, this would constitute a partial intervention, and reduce potential differences between intervention and control sites.

Hence recording of outcomes at control and intervention sites must rely on simple measures that can be implemented with minimal training, prior to the start of the trial at all sites. It is important that the procedures to ascertain (measure) these outcomes be established at the beginning of Phase 1, and continue **unchanged** at all health facilities (both intervention and control facilities) through-out the 18 months of the study.

Identification of contacts may not be performed, or not clearly recorded at all health facilities – especially the control facilities. This is why we must carefully document the number of index patients with active pulmonary TB diagnosed at each site. When the study is completed, the coordinating centre may use the number of index cases to estimate the number of household contacts that likely could have been identified (see Analysis section) Data sources will vary by site, depending what methods of documentation are already being used. We will collect information on the number of newly diagnosed index cases from lab or other sources that report active cases. The number of household contacts indentified will come from different sources depending on what is available the site. Finally, we will estimate the number of contacts who start LTBI treatment from hospital and or clinic records using a standard data collection form in all sites. The number of contacts completing LTBI therapy will be estimated retrospectively from clinic records.

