The resources and prior staff experience in LTBI care at the Canadian sites are very different from that of the sites in the LMIC. This makes it likely there will be better pre-intervention outcomes in Canada, potentially limiting the need for, and impact of certain interventions. The other 5 countries are also different – with regard to resources, availability of trained health workers, and patient populations. This may result in large differences in the baseline situation, and intervention effect size. Hence secondary analysis is planned to estimate the intervention effect within each country. Since Canada has the smallest numbers we estimated the power to detect differences in Canada alone, as shown in Table 3.

**Table 3: Detectable differences in Canada alone** (alpha=.05, and Power = 80% )

Proportion starting LTBI therapy in Control Arms	N Contacts per clinic	Design Effect	Total sample size per arm	Intra-Class Correlation	Detectable difference
0.30	50	1.5	150	0.01	0.19
0.30	50	3.5	150	0.05	0.29
0.30	50	5.9	150	0.10	0.37
0.30	100	2.0	300	0.01	0.16
0.30	100	6.0	300	0.05	0.27
0.30	100	10.9	300	0.10	0.36

Therefore in Canada, we should have sufficient power to detect a 27% increase in proportion of infected contacts starting LTBI therapy, if 30% now start therapy. Increasing the number of contacts per cluster (clinic) to 300 would only decrease the detectable difference to 25%.

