### **Data Analysis:**

There are three main comparisons:

First, we will compare the results at the original intervention clinics, from the last 6 months of the Primary study with the last 6 months of the secondary study - to assess whether any benefits found are sustained over time.

Second, we will assess the increase in contacts seen, investigated, started and completing LTBI treatment at the former control sites by comparing these numbers in the last 6 months of the Primary study with the last 6 months of the Secondary study.

As before, our analysis will be performed at the level of the individual, but will account for correlation between subjects from the same centre. Population averaged logistic regression with an identity link estimated via generalized estimating equations (GEE) and using a jack-knife estimate of the variance will be used to assess the effect of the intervention on the primary and secondary outcomes above, depending on the type of outcome (e.g. count or proportion). This approach will account for the correlation between subjects in the same cluster, and for varying cluster sizes. Using an identity link (rather than a logit link) will allow us to estimate risk differences for binary outcomes.

Population averaged models estimated via GEE are robust to mis-specification of the correlation structure. While our data will surely have clustering at the household level as well, we need only account for the top-level cluster (here centre) and use the empirical standard errors to ensure that our inferences are conservative.

For count type outcomes, we will use a similar approach as described above, but using a Poisson distribution.

In secondary analyses, we will use logistic regression with a logit link estimated via GEE and also adjust for additional confounders (country, age, sex and smear status of index case). In sensitivity analyses we will analyze at the level of the cluster. Missing data will be dealt with via multiple imputation using chained equations which will allow us to impute binary as well as continuous variables.

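### The main model for the two cross-over before-after comparisons has no clinic term, so a change in clinics' shares of identified contacts can bias the estimated change in proportions

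*Protocol*

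**What the plan says.** The Data Analysis section of the cross-over study (Protocol, Secondary Study) lists three comparisons. The first two are before-after contrasts in fixed sets of clinics. For persistence, "we will compare the results at the original intervention clinics, from the last 6 months of the Primary study with the last 6 months" (the latter in the cross-over). For the streamlined package, "we will assess the increase in contacts seen, investigated, started and completing LTBI treatment at the former control sites", over the same two windows. With an 18-month trial and a 12-month cross-over, these are months 13-18 and 25-30.

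The model follows: "As before, our analysis will be performed at the level of the individual, but will account for correlation between subjects from the same centre". It is "Population averaged logistic regression with an identity link estimated via generalized estimating equations (GEE) and using a jack-knife estimate of the variance", in the same words as the between-arm analysis under Data Analysis for Phase 2. Centre is a source of correlation only. The working correlation structure is not named; the text says "Population averaged models estimated via GEE are robust to mis-specification of the correlation structure".

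Three supporting provisions belong to the same plan:
- a Poisson version for counts;
- secondary logit-link models adjusted for country, age, sex and index-case smear status;
- a cluster-level sensitivity analysis, with pairing and weighting unstated.

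The denominator of the main proportion, set under Contact investigation outcomes, is identified contacts.

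**The concern.** In the randomised comparison, allocation stratified by country and restricted for balance protects the contrast between arms, so clinic can stay in the variance. Between two calendar windows nothing holds each clinic's share of contacts constant. If clinics differ in their start proportion and their shares move, a model with a period term alone can read the movement as change.

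The protocol gives reason to expect both conditions. On differences between countries, the sample size section says "This may result in large differences in the baseline situation, and intervention effect size" and expects better outcomes in Canada. On the denominator, the section on ascertainment says "Identification of contacts may not be performed, or not clearly recorded at all health facilities", especially at control sites. The package targets identification, and the second comparison itself expects more contacts to be seen.

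Secondary objectives 3 and 4 (sustained effect; costs and impact of the streamlined package) rest on these contrasts. The costs section defines additional contacts from the pre-post difference in proportion. If the cross-over cost-effectiveness ratio uses that definition, reading +2.7 for a true +5.0 raises the cost per added contact by 5.0/2.7, about 1.8-fold.

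**Working it through.** **The plan's own figures.** The protocol gives no calculation for the cross-over comparisons. The nearest is Table 2 (0.10 v 0.20, ICC 0.05, 100 contacts per clinic). The usual two-proportion formula gives 199 per arm, and 199 x (1 + 99 x 0.05) = 199 x 5.95 = 1184, against 1214 stated. That is within 3%, so the ICC and cluster size are used below as the protocol means them.

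**Clinic sizes.** Table 1 contacts / units / 3 gives contacts per clinic per six months: Canada 1575/4/3 = 131.25; Benin 3150/2/3 = 525; Ghana 1900/2/3 = 316.7; Indonesia and Vietnam 1900/8/3 = 79.2. Half of the 24 units is 2 Canadian clinics (262.5 contacts) and 10 LMIC clinics (525 + 316.7 + 8 x 79.2 = 1475).

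**What the period-only model estimates.** Let w be a clinic's share of contacts and p its start proportion. Under independence:

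estimate = sum(w_after x p_after) - sum(w_before x p_before) = sum(w_after x change in p) + sum(change in w x p_before).

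The second term is pure mix.

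**Assumed scenarios.** None of the identification or start rates below is in the protocol. Canada identifies 90% of contacts in both windows (236.25), and every clinic has the same true change.

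- (a) LMIC identification 50% to 90%; Canada 30% to 40%, LMIC 10% to 20%; truth +10. Canadian share 236.25/973.75 = 24.3% before, 236.25/1563.75 = 15.1% after. Mix term (0.1511 - 0.2426) x 0.20 = -1.8 points.
- (b) Same shift; Canada 30% to 35%, LMIC 5% to 10%; truth +5. Mix term -0.0915 x 0.25 = -2.3 points.
- (c) LMIC identification 90% to 45%; Canada 45% to 42%, LMIC 20% to 17%; truth -3. Canadian share 15.1% to 236.25/900 = 26.3%. Mix term +0.1114 x 0.25 = +2.8 points.

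**Exchangeable structure.** For a clinic with N contacts over both windows, the inverse working correlation is proportional to I - [r/(1 + (N-1)r)]J. As N x r grows, this approaches subtraction of the clinic mean, which is close to a clinic fixed effect.

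Estimates in percentage points:

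| | Truth | Independence | Exchangeable, r 0.01 to 0.02 | Exchangeable, r 0.05 to 0.10 | Exchangeable, r estimated | Clinic fixed effects |
|---|---|---|---|---|---|---|
| (a) | +10 | +8.2 | 9.46 to 9.64 | 9.78 to 9.83 | 9.7 | 9.9 |
| (b) | +5 | +2.7 | 4.32 to 4.56 | 4.74 to 4.80 | 4.8 | 4.9 |
| (c) | -3 | -0.2 | -2.16 to -2.49 | -2.75 to -2.85 | -2.6 | -2.9 |

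The last two columns are fits to whole counts; the fixed-effect departures from the truth are rounding of counts.

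**No true change in any clinic.** With assumed start rates of 60% in Canada, 40% in Benin, 20% in Ghana and Indonesia and 10% in Vietnam, doubling Indonesian and Vietnamese contacts gives -4.1 points under independence, -0.1 under exchangeable and 0.0 with clinic indicators. With Benin at 50% and the rest at 20%, Benin x 1.5 and Indonesia and Vietnam halved give +4.9, 0.0 and 0.0. The error can go either way.

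**The case against.** **Planned analyses already cover part of this.** All three scenarios shift Canada against the LMIC sites. An identity-link country term recovers +10, +5 and -3, and so do equally weighted clinic proportions. The planned country adjustment would remove this mix too, although its logit link gives an odds ratio (about 2.0, 1.7 and 0.84), not the risk difference, and it leaves shifts between clinics within a country. The cluster-level analysis works if clinics are paired or weighted equally, which is not stated. Both are back-ups. If they disagreed with the main model, the main estimate would still be the one planned.

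**The size rests on an unnamed working correlation.** This stands, and it limits the point. A reader might infer that the comparisons are biased by several points as planned. The protocol does not support that: an exchangeable structure at its own ICC range removes most of the error. Its statement about robustness does not settle the matter, because with a period-only mean model and changing clinic shares the chosen structure moves the point estimate, not only the standard error.

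**A reader might infer that the streamlined benefit is understated or a decline is hidden.** Either can happen; neither follows. Direction depends on the shift. Contacts identified is itself a listed outcome, and in (c) it falls from about 1,564 to 900, with starts from 372 to 212. The protocol also allows contacts to be estimated from index cases. On that denominator (c) goes from 372/1737.5 to 212/1737.5, about -9 points, and unequal identification no longer shifts the weights.

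**A reader might expect a clinic term to sharpen the estimate.** In simulation it cut the SD by 26% to 39% against independence. Against exchangeable weights at 0.05 the SDs were equal (1.83 v 1.83 points with no shift). The gain is not specific to a clinic term.

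**Counts and stability.** The second comparison is partly worded as numbers, to which the mix argument does not apply. The recruitment section expects no major change in contact numbers, but that rests on TB caseload, not on the share of contacts identified.

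**Conclusion.** The point holds for proportions among identified contacts. A between-arm model is reused for within-clinic comparisons, and its main version leaves the period estimate open to changes in clinics' shares of contacts. Under independence and the assumed shifts the error is about 2 to 3 points. Under an exchangeable structure at an ICC of 0.05 to 0.10 it is about 0.2 to 0.4 points. At 0.01 to 0.02, the range the protocol reports for treatment completion in the earlier trial, it is about 0.4 to 0.8 points.

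These sizes rest on Table 1 volumes, 12 clinics per comparison, equal true change in every clinic, and identification and start rates that are assumptions. The protocol expects effects to differ between countries, so the figures are illustrations, not forecasts. The randomised primary comparison is not affected. The change is worth making because secondary objectives rest on these contrasts, and one permitted choice would read (c) as sustained while another would read it as a decline.

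**What to change.** In the cross-over Data Analysis section, make the main analysis of the first two comparisons within clinic. Either:

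- fit the identity-link model with a fixed effect for each clinic plus a period term, keeping the jack-knife over clinics; or
- take the mean of the paired clinic differences in proportion, with a paired t interval.

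State which is the main estimate: with unequal effects across clinics the first gives larger clinics more weight and the second weights clinics equally. Keep the clinic term if the other arm is added as a comparison.

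The cost is one sentence of analysis wording, no new data, and about 12 clinic parameters per comparison. One small downside: a clinic with no identified contacts in one window contributes nothing to the contrast and should be reported separately. The change does not remove secular trend, which has no concurrent control in either comparison as written; the report should say so.

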### **Ethical Issues:**

The ethical concerns over with-holding the intervention at control sites will be addressed by introducing the full intervention package to the control sites at the end of the 18 months primary study. At this time we will take advantage of the experience gained and lessons learned from the primary study to introduce what should be a more streamlined, effective and cost-effective set of interventions - providing enhanced benefit to these populations. Consent will not be sought - for the same reasons explained above, and all measures to protect confidentiality will remain in place.

### **3. TRIAL OVERSIGHT AND ROLE OF INVESTIGATORS**

#### **3.1 Day to Day management:**

The study will be managed in each country by the Country Principal Investigators. Randomization will be overseen by the trial biostatistician – [name]. [name] and [name] will be involved in adapting the questionnaires developed in Brazil to the other countries' settings and populations.

### **4. IMPORTANCE OF THE STUDY AND NEXT STEPS**

The proposed study will establish a firm methodological foundation and establish the feasibility of this complex public health approach in Canada and five low or middle income countries. The questionnaires and other instruments including the contact registries, treatment cards and reporting forms will be developed and validated by the end of this study. These instruments can then be adapted and translated for use in many other countries to assess the barriers to successful contact investigation and management. These can be used immediately to scale up this activity through-out the countries involved in the study, and also introduced in other countries to identify key problems and potential solutions in those settings. We will also have developed an important tool for eventual use by National TB programmes within many LMIC – the Contact Management Registries and their related quarterly reporting mechanisms. These registries and reports are modeled after registries and reports used for active TB by NTP in many LMIC.

At the end of Phase 2 we will have established the feasibility, as well as identified all costs related to the implementation of a package of interventions to improve contact investigation. We will also have refined the approach to training and supervision, based on our experience. Given the potential impact of contact investigation and treatment on TB prevention activities, this pragmatic package may offer a blue-print for global action to help meet the World Health Organization's post-2015 targets for TB elimination.

